**Table 26: DOOR Probability and 95% Confidence Interval by Day 8 – ITT Population, Stage 2a and 2b**

Subjects With Non-missing DOOR – n (%)	Subjects With Missing DOOR – n (%)	DOOR Probability With IPW a (95% CI) b	DOOR Probability Without IPW c (95% CI) b
x (x)	x (x)	x.xx (x.xx, x.xx)	x.xx (x.xx, x.xx)

aProbability of more desirable DOOR in IV bacteriophage + 0.5 (probability of equal DOOR) using the greatest reduction in *P. aeruginosa* CFU/mL by Day 8. This analysis uses IPW to handle the impact of missing values of DOOR.

b95% CI calculated using the method in Halperin et. al Superiority of IV bacteriophage vs. placebo is concluded if the lower bound of the 95% CI for the DOOR probability is above 0.5.

cThis calculation does not use inverse probability weighting to handle missing DOOR values.

**Table 27: Sensitivity Analysis of DOOR by Day 8 – ITT Population, Stage 2a and 2b**

Imputed DOOR Ranks in Placebo	Imputed DOOR Ranks in IV Bacteriophage					
	1:0%, 2:0%, 3:0%, 4:100%	1:0%, 2:0%, 3:40%, 4:60%	1:20%, 2:20%, 3:40%, 4:20%	1:20%, 2:40%, 3:20%, 4:20%	1:60%, 2:40%, 3:0%, 4:0%	1:100%, 2:0%, 3:0%, 4:0%
1:0%, 2:0%, 3:0%, 4:100%	xx (xx, xx)	xx (xx, xx)	xx (xx, xx)	xx (xx, xx)	xx (xx, xx)	xx (xx, xx)
1:0%, 2:0%, 3:40%, 4:60%	xx (xx, xx)	xx (xx, xx)	xx (xx, xx)	xx (xx, xx)	xx (xx, xx)	xx (xx, xx)
1:20%, 2:20%, 3:40%, 4:20%	xx (xx, xx)	xx (xx, xx)	xx (xx, xx)	xx (xx, xx)	xx (xx, xx)	xx (xx, xx)
1:20%, 2:40%, 3:20%, 4:20%	xx (xx, xx)	xx (xx, xx)	xx (xx, xx)	xx (xx, xx)	xx (xx, xx)	xx (xx, xx)
1:60%, 2:40%, 3:0%, 4:0%	xx (xx, xx)	xx (xx, xx)	xx (xx, xx)	xx (xx, xx)	xx (xx, xx)	xx (xx, xx)
1:100%, 2:0%, 3:0%, 4:0%	xx (xx, xx)	xx (xx, xx)	xx (xx, xx)	xx (xx, xx)	xx (xx, xx)	xx (xx, xx)

Note: Values shown are the DOOR probability, i.e., the probability of more desirable DOOR in IV bacteriophage arm + 0.5 (probability of equal DOOR) using the greatest reduction in *P. aeruginosa* CFU/mL by Day 8, and the associated 95% CI obtained through the method described in Halperin et. al.

**Table 28: Distribution of DOOR Categories by Treatment Group and Time Point – ITT Population, Stage 2a and 2b**

[Implementation note: ‘Selected IV Bacteriophage Dose’ will be replaced with the dose chosen by the interim analysis.]

Time Point	DOOR Rank	Selected IV Bacteriophage Dose (N=X)		Placebo (N=X)	
		n	%	n	%
Day 1 Post-infusion	Any Rank	x	xx	x	xx
	Rank 1: No SAE (related to study product) and $> 2 \log_{10}$ reduction in P. aeruginosa CFU/mL	x	xx	x	xx
	Rank 2: No SAE (related to study product) and 1-2 $\log_{10}$ reduction in P. aeruginosa CFU/mL	x	xx	x	xx
	Rank 3: No SAE (related to study product) and $< 1 \log_{10}$ reduction in P. aeruginosa CFU/mL	x	xx	x	xx
	Rank 4: SAE (related to study product)	x	xx	x	xx
	Missing	x	xx	x	xx
Day 2	Any Rank	x	xx	x	xx
	Rank 1: No SAE (related to study product) and $> 2 \log_{10}$ reduction in P. aeruginosa CFU/mL	x	xx	x	xx
	Rank 2: No SAE (related to study product) and 1-2 $\log_{10}$ reduction in P. aeruginosa CFU/mL	x	xx	x	xx
	Rank 3: No SAE (related to study product) and $< 1 \log_{10}$ reduction in P. aeruginosa CFU/mL	x	xx	x	xx
	Rank 4: SAE (related to study product)	x	xx	x	xx
	Missing	x	xx	x	xx
Day 5	Any Rank	x	xx	x	xx
	Rank 1: No SAE (related to study product) and $> 2 \log_{10}$ reduction in P. aeruginosa CFU/mL	x	xx	x	xx
	Rank 2: No SAE (related to study product) and 1-2 $\log_{10}$ reduction in P. aeruginosa CFU/mL	x	xx	x	xx
	Rank 3: No SAE (related to study product) and $< 1 \log_{10}$ reduction in P. aeruginosa CFU/mL	x	xx	x	xx
	Rank 4: SAE (related to study product)	x	xx	x	xx
	Missing	x	xx	x	xx
Day 8	Any Rank	x	xx	x	xx
	Rank 1: No SAE (related to study product) and $> 2 \log_{10}$ reduction in P. aeruginosa CFU/mL	x	xx	x	xx
	Rank 2: No SAE (related to study product) and 1-2 $\log_{10}$ reduction in P. aeruginosa CFU/mL	x	xx	x	xx
	Rank 3: No SAE (related to study product) and $< 1 \log_{10}$ reduction in P. aeruginosa CFU/mL	x	xx	x	xx
	Rank 4: SAE (related to study product)	x	xx	x	Xx
	Missing	x	xx	x	xx
Maximum a	Any Rank	x	xx	x	xx
	Rank 1: No SAE (related to study product) and $> 2 \log_{10}$ reduction in P. aeruginosa CFU/mL	x	xx	x	xx
	Rank 2: No SAE (related to study product) and 1-2 $\log_{10}$ reduction in P. aeruginosa CFU/mL	x	xx	x	xx
	Rank 3: No SAE (related to study product) and $< 1 \log_{10}$ reduction in P. aeruginosa CFU/mL	x	xx	x	xx
	Rank 4: SAE (related to study product)	x	xx	x	Xx
	Any Rank	x	xx	x	xx

Notes: N=Number of subjects in the ITT Population in Stage 2a and 2b.

n=Number of subjects in the corresponding analysis population, treatment group, and DOOR rank

aMaximum rows show DOOR ranks using greatest  $\log_{10}$  reduction in *P. aeruginosa* CFU/mL by Day 8.

**Table 29: Subgroup Analysis of DOOR at Day 8 – ITT Population, Stage 2a and 2b**

[Implementation note: ‘Organism X’ will be replaced with any organisms recovered on sputum cultures with one yes/no row for each organism.]

Subgroup	Subjects With Non-missing DOOR – $n_b$ (%)	Subjects With Non-missing DOOR – $n_p$ (%)	Subjects With Missing DOOR – $n_b$ (%)	Subjects With Missing DOOR – $n_p$ (%)	DOOR Probability With IPW a (95% CI) b	DOOR Probability Without IPW c (95% CI) b
Susceptible to Bacteriophages – Yes	x (x)	x (x)	x (x)	x (x)	x.xx (x.xx, x.xx)	x.xx (x.xx, x.xx)
Susceptible to Bacteriophages – No	x (x)	x (x)	x (x)	x (x)	x.xx (x.xx, x.xx)	x.xx (x.xx, x.xx)
Presence of Co-infection with Organism X – Yes	x (x)	x (x)	x (x)	x (x)	x.xx (x.xx, x.xx)	x.xx (x.xx, x.xx)
Presence of Co-infection with Organism X – No	x (x)	x (x)	x (x)	x (x)	x.xx (x.xx, x.xx)	x.xx (x.xx, x.xx)

Notes:  $n_b$ =number of subjects in the ITT population in Stage 2a and 2b who received IV bacteriophage within the subgroup category.  $n_p$ =number of subjects in the ITT population who received placebo within the subgroup category. Denominator for percentages is the total number of IV bacteriophage subjects in the ITT population for  $n_b$  and the total number of placebo subjects in the ITT population for  $n_p$ .

aProbability of more desirable DOOR in IV bacteriophage arm + 0.5 (Probability of Equal DOOR) using the greatest reduction in *P. aeruginosa* CFU/mL by Day 8. This analysis uses IPW to handle the impact of missing values of DOOR.

b95% CI calculated using the method in Halperin et. al. Superiority of IV bacteriophage vs placebo is concluded if the lower bound of the 95% CI for the DOOR probability is above 0.5.

cThis calculation does not use inverse probability weighting to handle missing DOOR values.

**Table 30: Distribution of DOOR Categories by Subgroup, Treatment Group, and Time Point – ITT Population, Stage 2a and 2b**

[Implementation note: ‘Selected IV Bacteriophage Dose’ will be replaced with the dose chosen by the interim analysis.]

Subgroup	DOOR Rank	Selected IV Bacteriophage Dose (N=X)		Placebo (N=X)	
		n	%	n	%
Day 1 Post-infusion					
Susceptible to Bacteriophages - Yes	Any Rank				
	Rank 1: No SAE (related to study product) and $> 2 \log_{10}$ reduction in P. aeruginosa CFU/mL	x	xx	x	xx
	Rank 2: No SAE (related to study product) and 1-2 $\log_{10}$ reduction in P. aeruginosa CFU/mL	x	xx	x	xx
	Rank 3: No SAE (related to study product) and $< 1 \log_{10}$ reduction in P. aeruginosa CFU/mL	x	xx	x	xx
	Rank 4: SAE (related to study product)	x	xx	x	xx
	Missing	x	xx	x	xx
Susceptible to Bacteriophages - No	Any Rank	x	xx	x	xx
	Rank 1: No SAE (related to study product) and $> 2 \log_{10}$ reduction in P. aeruginosa CFU/mL	x	xx	x	xx
	Rank 2: No SAE (related to study product) and 1-2 $\log_{10}$ reduction in P. aeruginosa CFU/mL	x	xx	x	xx
	Rank 3: No SAE (related to study product) and $< 1 \log_{10}$ reduction in P. aeruginosa CFU/mL	x	xx	x	xx
	Rank 4: SAE (related to study product)	x	xx	x	xx
	Missing	x	xx	x	xx
Presence of Co-infection with Organism X - Yes	Any Rank	x	xx	x	xx
	Rank 1: No SAE (related to study product) and $> 2 \log_{10}$ reduction in P. aeruginosa CFU/mL	x	xx	x	xx
	Rank 2: No SAE (related to study product) and 1-2 $\log_{10}$ reduction in P. aeruginosa CFU/mL	x	xx	x	xx
	Rank 3: No SAE (related to study product) and $< 1 \log_{10}$ reduction in P. aeruginosa CFU/mL	x	xx	x	xx
	Rank 4: SAE (related to study product)	x	xx	x	xx
	Missing	x	xx	x	xx

**Table 30: Distribution of DOOR Categories by Subgroup, Treatment Group, and Time Point – ITT Population, Stage 2a and 2b (continued)**

Subgroup	DOOR Rank	Selected IV Bacteriophage Dose (N=X)		Placebo (N=X)	
		n	%	n	%
Presence of Co-infection with Organism X - No	Any Rank	x	xx	x	xx
	Rank 1: No SAE (related to study product) and $> 2 \log_{10}$ reduction in P. aeruginosa CFU/mL	x	xx	x	xx
	Rank 2: No SAE (related to study product) and 1-2 $\log_{10}$ reduction in P. aeruginosa CFU/mL	x	xx	x	xx
	Rank 3: No SAE (related to study product) and $< 1 \log_{10}$ reduction in P. aeruginosa CFU/mL	x	xx	x	xx
	Rank 4: SAE (related to study product)	x	xx	x	xx
	Missing	x	xx	x	xx
Day 2					
...					
Day 5					
...		x	xx	x	xx
Day 8					
...		x	xx	x	Xx
Maximuma					
...					

Notes: N=Number of subjects in the ITT population in Stage 2a and 2b in the given treatment group.

n=Number of subjects in the corresponding analysis population, treatment group, and DOOR rank.

aMaximum rows show DOOR ranks using greatest  $\log_{10}$  reduction in *P. aeruginosa* CFU/mL by Day 8.

**Table 31: Cumulative Proportions of DOOR Categories - ITT Analysis Population, Stage 2a and 2b**

[Implementation note: ‘Selected IV Bacteriophage Dose’ will be replaced with the dose chosen by the interim analysis.]

Time Point	DOOR Rank	Selected IV Bacteriophage Dose (N=X)			Placebo (N=X)	
		n (%)	Cumulative n (%) a	Cumulative Dichotomized Pr(DOOR) a,b (95% CI) c	n (%)	Cumulative n (%) a
Day 1 Post-infusion	Rank 1: No SAE (related to study product) and > 2 log 10 reduction in P. aeruginosa CFU/mL	x (x)	x (x)	x.x (x.x, x.x)	x (x)	x (x)
	Rank 2: No SAE (related to study product) and 1-2 log 10 reduction in P. aeruginosa CFU/mL	x (x)	x (x)	x.x (x.x, x.x)	x (x)	x (x)
	Rank 3: No SAE (related to study product) and <1 log 10 reduction in P. aeruginosa CFU/mL	x (x)	x (x)	x.x (x.x, x.x)	x (x)	x (x)
	Rank 4: SAE (related to study product)	x (x)	x (x)	-	x (x)	x (x)
	Missing	x (x)	-	-	x (x)	-
Day 2	Rank 1: No SAE (related to study product) and > 2 log 10 reduction in P. aeruginosa CFU/mL	x (x)	x (x)	x.x (x.x, x.x)	x (x)	x (x)
	Rank 2: No SAE (related to study product) and 1-2 log 10 reduction in P. aeruginosa CFU/mL	x (x)	x (x)	x.x (x.x, x.x)	x (x)	x (x)
	Rank 3: No SAE (related to study product) and <1 log 10 reduction in P. aeruginosa CFU/mL	x (x)	x (x)	x.x (x.x, x.x)	x (x)	x (x)
	Rank 4: SAE (related to study product)	x (x)	x (x)	-	x (x)	x (x)
	Missing	x (x)	-	-	x (x)	-
Day 5	Rank 1: No SAE (related to study product) and > 2 log 10 reduction in P. aeruginosa CFU/mL	x (x)	x (x)	x.x (x.x, x.x)	x (x)	x (x)
	Rank 2: No SAE (related to study product) and 1-2 log 10 reduction in P. aeruginosa CFU/mL	x (x)	x (x)	x.x (x.x, x.x)	x (x)	x (x)
	Rank 3: No SAE (related to study product) and <1 log 10 reduction in P. aeruginosa CFU/mL	x (x)	x (x)	x.x (x.x, x.x)	x (x)	x (x)
	Rank 4: SAE (related to study product)	x (x)	x (x)	x.x (x.x, x.x)	x (x)	x (x)
	Missing	x (x)	-	-	x (x)	-
Day 8	Rank 1: No SAE (related to study product) and > 2 log 10 reduction in P. aeruginosa CFU/mL	x (x)	x (x)	x.x (x.x, x.x)	x (x)	x (x)
	Rank 2: No SAE (related to study product) and 1-2 log 10 reduction in P. aeruginosa CFU/mL	x (x)	x (x)	x.x (x.x, x.x)	x (x)	x (x)
	Rank 3: No SAE (related to study product) and <1 log 10 reduction in P. aeruginosa CFU/mL	x (x)	x (x)	x.x (x.x, x.x)	x (x)	x (x)
	Rank 4: SAE (related to study product)	x (x)	x (x)	-	x (x)	x (x)
	Missing	x (x)	-	-	x (x)	-

**Table 31: Cumulative Proportions of DOOR Categories - ITT Analysis Population, Stage 2a and 2b (continued)**

Maximum d	Rank 1: No SAE (related to study product) and $> 2 \log_{10}$ reduction in P. aeruginosa CFU/mL	x (x)	x (x)	x.x (x.x, x.x)	x (x)	x (x)
	Rank 2: No SAE (related to study product) and 1-2 $\log_{10}$ reduction in P. aeruginosa CFU/mL	x (x)	x (x)	x.x (x.x, x.x)	x (x)	x (x)
	Rank 3: No SAE (related to study product) and $< 1 \log_{10}$ reduction in P. aeruginosa CFU/mL	x (x)	x (x)	x.x (x.x, x.x)	x (x)	x (x)
	Rank 4: SAE (related to study product)	x (x)	x (x)	-	x (x)	x (x)
	Missing	x (x)	-	-	x (x)	-

Notes: N=Number of subjects in the ITT Population in the given treatment group.

n=Number of subjects in the corresponding analysis population, treatment group, and DOOR rank

aCumulative n and percent do not include missing data.bProbability of more desirable DOOR rank in IV Bacteriophage arm at each respective day + 0.5(Probability of Equal DOOR rank).c95% CI calculated using the method in Halperin et. al.dMaximum rows show DOOR ranks using greatest  $\log_{10}$  reduction in *P. aeruginosa* CFU/mL by Day 8.

**Table 32: Difference in Mean Partial Credit for DOOR Categories Through Day 8 – ITT Population, Stage 2a and 2b**

[Implementation note: ‘Selected IV Bacteriophage Dose’ will be replaced with the dose chosen by the interim analysis. The 95% CI for the difference in means is computed from Welch’s t-test]

Scenario	Time Point	Treatment Group	n	Mean (SD)	Difference in Means (95% CI) a
A: (1=100, 2=100, 3=100, 4=0)	Day 1 Post-infusion	Selected IV Bacteriophage Dose (N=X)	xx	xx (xx.x)	xx (xx.x, xx.x)
		Placebo (N=X)	xx	xx (xx.x)	
	Day 2	Selected IV Bacteriophage Dose (N=X)	xx	xx (xx.x)	xx (xx.x, xx.x)
		Placebo (N=X)	xx	xx (xx.x)	
	Day 5	Selected IV Bacteriophage Dose (N=X)	xx	xx (xx.x)	xx (xx.x, xx.x)
		Placebo (N=X)	xx	xx (xx.x)	
	Day 8	Selected IV Bacteriophage Dose (N=X)	xx	xx (xx.x)	xx (xx.x, xx.x)
		Placebo (N=X)	xx	xx (xx.x)	
	Maximum	Selected IV Bacteriophage Dose (N=X)	xx	xx (xx.x)	xx (xx.x, xx.x)
		Placebo (N=X)	xx	xx (xx.x)	

[Extend the table to add Scenarios B: (1=100, 2=100, 3=0, 4=0) and C: (1=100, 2=0, 3=0, 4=0)]

Notes: N=Number of subjects in the ITT population in Stage 2a and 2b.

n=Number of subjects in the corresponding analysis population with non-missing values of partial credit scores.

SD=Standard Deviation.

aThe 95% CI for the difference in means is computed from Welch’s t-test.

**Table 33: Summary of DOOR Components Through Day 8 - ITT Analysis Population, Stage 2a and 2b**

[Implementation note: ‘Selected IV Bacteriophage Dose’ will be replaced with the dose chosen by the interim analysis.]

DOOR Component	Selected IV Bacteriophage Dose (N=X)			Placebo (N=X)	
	n (%)	Cumulative n (%)	Cumulative Dichotomized Pr(DOOR) a (95% CI) b	n (%)	Cumulative n (%)
Day 1 Post-infusion					
SAE					
No SAE (related to study product)	x (x)	x (x)	x.x (x.x, x.x)	x (x)	x (x)
SAE	x (x)	x (x)	-	x (x)	x (x)
DOOR Probability for SAE Component c	x (100)	x (100)	x.x (x.x, x.x)	x (100)	x (100)
log10 Reduction in P. aeruginosa CFU/mL					
>2 log 10 reduction in P. aeruginosa CFU/mL	x (x)	x (x)	x.x (x.x, x.x)	x (x)	x (x)
1-2 log 10 reduction in P. aeruginosa CFU/mL	x (x)	x (x)	x.x (x.x, x.x)	x (x)	x (x)
<1 log 10 reduction/increase in P. aeruginosa CFU/mL	x (x)	x (x)	-	x (x)	x (x)
DOOR Probability for log10 Reduction in P. aeruginosa CFU/mL Component	x (100)	x (100)	x.x (x.x, x.x)	x (100)	x (100)
Day 2					
...					
Day 5					
...					
Day 8					
...					
Maximum d					
...					

Notes: N=Number of subjects in the ITT population in Stage 2a and 2b with sputum collected at the given time point.

n=Number of subjects in the corresponding analysis population, treatment group, and DOOR category at the given time point.

aProbability of more desirable DOOR component rank in IV Bacteriophage arm at each respective day + 0.5(Probability of Equal DOOR component rank). Dichotomized Pr(DOOR) of multiclass DOOR components classify the respective row class and more desirable classes (if any) as equally desirable.b95% CI calculated using the method in Halperin et. al.cBecause the SAE Component is dichotomous, the DOOR Probability for that component and the Cumulative Dichotomized Pr(DOOR) should be equal.dMaximum rows show DOOR ranks using greatest log10 reduction in *P. aeruginosa* CFU/mL by Day 8.

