6.3.3 Early Termination Visit

If a subject terminates or is withdrawn from the study prior to the final Follow-up Visit, all attempts will be made to collect the following as part of an Early Termination Visit:

- Review of systems
- Review concomitant medications
- Symptom directed physical examination
- Spirometry*
- Vital signs
- Sputum collection (to be completed after spirometry, as determined necessary by the local investigator to increase sputum production) for microbiological and PK assessments
- Hematology (see Section 7.2.1 for complete list of tests)*
- Clinical chemistry (see Section 7.2.1 for complete list of tests)*
- Liver function tests (see Section 7.2.1 for complete list of tests)*
- CFRSD, preferably before the collection of study data (**Stage 2 only**). If subject is ready to produce sputum, prioritize sputum collection over administration of the CFRSD.
- Clinical assessment of AEs

- Events of special interest [ESIs] (i.e., pulmonary exacerbations), if this visit occurs prior to Visit 5, Day 8 + 3 days (see Section 8.2.2)

**If the visit occurs > 7 days after a scheduled visit. If the visit occurs ≤ 7 days after a scheduled visit, laboratory tests may be collected and spirometry may be performed at the discretion of the local investigator.*

If a subject is considered by the local investigator to be too ill to attend an in-person or virtual Early Termination Visit, this visit may be conducted by telephone call.

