### 3.3. Study Definitions and Derived Variables

#### 3.3.1. Definitions for the DOOR Endpoint

Most desirable	Rank 1	No SAE (related to study product) and $> 2 \log_{10}$ reduction in P. aeruginosa CFU/mL
↑	Rank 2	No SAE (related to study product) and $1-2 \log_{10}$ reduction in P. aeruginosa CFU/mL
↓	Rank 3	No SAE (related to study product) and $< 1 \log_{10}$ reduction in P. aeruginosa CFU/mL
Least desirable	Rank 4	SAE (related to study product)

Abbreviations: CFU: colony-forming units; mL: milliliter; SAE: serious adverse events.

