## 8. MICROBIOLOGICAL ACTIVITY AND BENEFIT TO RISK PROFILE EVALUATION

All variables in the microbiological activity and benefit to risk profile analyses will be listed by subject. Data will be summarized by treatment group. Continuous variables will be summarized with the number of observations, mean, median, SD, quartiles, minimum, and maximum. Categorical variables will be summarized by number and percent in each category. All microbiological activity and benefit to risk profile analyses will be performed using the ITT population.

This study does not include formal hypothesis testing for any of the primary endpoints, and instead relies on CIs for conclusions of treatment effects.

All microbiological activity and benefit to risk profile tables and figures will compare all subjects receiving placebo to all subjects receiving the selected dose of IV bacteriophage chosen from the interim analysis.

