- Cumulative proportions of DOOR categories through Day 8 + 3 for IV bacteriophage vs. placebo with cumulative DOOR probabilities and corresponding 95% CI ([Table 31](#)). This analysis compares the DOOR probability from the following dichotomizations of DOOR: first by calculating the dichotomized DOOR probability comparing those with DOOR rank = 1 to DOOR ranks 2, 3, and 4 pooled together, then DOOR rank 1 and 2 compared to DOOR rank 3 and 4, and finally comparing DOOR ranks 1, 2, and 3 to DOOR rank 4.
- Sequential dichotomization of DOOR will be presented in [Figure 12](#). Cumulative probabilities will be calculated using the following dichotomizations: rank 1 vs ranks 2, 3, and 4; ranks 1 and 2 vs ranks 3 and 4; and ranks 1, 2, and 3 vs rank 4.
- Comparison of each of the components of the DOOR between the IV bacteriophage and placebo arms through Day 8 with 95% CI, summarized by DOOR probability and 95% CI ([Table 33](#)). For the SAE component of DOOR the dichotomized DOOR probability will be calculated using ‘No SAE’ = rank 1 and ‘SAE’ = rank 2. For the log10 reduction component of DOOR the dichotomized DOOR probability will be calculated using ‘>2 log10 reduction in *P. aeruginosa* CFU/mL’ = rank 1, ‘1-2 log10 reduction in *P. aeruginosa* CFU/mL’ = rank 2, and ‘<1 log10 reduction in *P. aeruginosa* CFU/mL’ = rank 3.
- Forest plot of probabilities of DOOR and its components at Day 8 + 3 and corresponding 95% CI calculated using the method in Halperin et. al. [2] ([Figure 10](#)).
- Point estimate and CI of difference in mean partial credit vs. placebo through Day 8 and corresponding 95% CI ([Table 32](#)). The 95% CI will be calculated using Welch’s t-test. The partial credit analysis will be calculated assigning a grading key to each of the DOOR categories. The grading keys used will be the following: A: (DOOR rank 1 = 100, rank 2 = 100, rank 3 = 100, rank 4 = 0), B: (rank 1 = 100, rank 2 = 100, rank 3 = 0, rank 4 = 0), C: (rank 1 = 100, rank 2 = 0, rank 3 = 0, rank 4 = 0). For each scenario, the mean and SD of these partial credit scores will be provided for each treatment group and corresponding scenario.
- Difference in means of partial credit score by time point ([Figure 13](#)).

A listing of individual DOOR response data will be presented in [Listing 12](#).

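### Table 33 counts related SAEs only among subjects with sputum at the visit, so its visit-level SAE rows can omit a harmed subject whom the ITT rule would keep

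*SAP*

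**What the plan says.** SAP Table 33 reports the two DOOR components at Day 1 post-infusion, Days 2, 5 and 8, and in a Maximum block. One note sets the denominator for both components: "N=Number of subjects in the ITT population in Stage 2a and 2b with sputum collected at the given time point". The addendum on undetectable colony counts carries the same note under its Tables 26 and 27, the primary and sensitivity versions of this table.

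The numerator note does not mention sputum: "n=Number of subjects in the corresponding analysis population, treatment group, and DOOR category at the given time point". The SAE block has two categories and a closing row, "DOOR Probability for SAE Component", fixed at 100%. It has no Missing row. The footnote to the Maximum block says "Maximum rows show DOOR ranks using greatest" log10 reduction by Day 8, so that block is not a visit.

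Elsewhere the SAP sets a different basis:

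- Section 8: "All microbiological activity and benefit to risk profile analyses will be performed using the ITT population".
- Section 8.1.3: "For the SAE component of DOOR the dichotomized DOOR probability will be calculated using" a two-level rank, no SAE against SAE, with no sputum condition.
- Section 3.3.1: Rank 4 requires a related SAE and nothing else. Colony counts only separate Ranks 1 to 3.
- Tables 28 and 31: N is the ITT population, and the visit blocks carry a Missing row.

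Protocol 6.3.3 gives a route by which an ill subject can leave without a sample. For a subject considered "too ill to attend an in-person or virtual Early Termination Visit, this visit may be conducted by telephone call".

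**The concern.** A sputum-based denominator suits the log10-reduction rows, because a reduction cannot be computed without a sample. It does not suit the SAE rows. A related SAE is known whether or not the subject later produces sputum, and it may be the reason that the subject does not. Protocol 5.2.1 lists meeting the infusion-halting criteria among possible reasons for withdrawal, and a telephone termination visit yields no specimen. The harm itself can then remove the subject from the denominator against which harm is measured.

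The visit-level SAE comparison would then be biased toward no harm, in favour of whichever arm has SAEs that prevent sampling. The component display could also disagree with the composite displays, where the same subject is Rank 4.

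**Working it through.** Table 33 is an empty shell, so there is no planned figure to reproduce. The check is whether the note really removes the subject, and by how much the rows then change.

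**Inputs.** Planned n per arm is 20 (Protocol 10.2) and the maximum is 25 (SAP section 5). Intervals are two-sided 95%, using the Halperin formulas of SAP 8.1.3. The documents give no related-SAE rate. The assumption is k related SAEs on phage, none on placebo, no sputum from those k subjects at the visit, and sputum from everyone else. The range shown is k = 1 to 3.

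**Step 1: does the note drop the subject?** The numerator note alone could be read as keeping the subject. With n = 20 and k = 1, that puts 19 (no SAE) + 1 (SAE) = 20 subjects over N = 19, which is 105%. The shell fixes the total at 100%. The stated N and the stated total can both hold only if the subject is in neither row.

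**Step 2: formula.** For a binary component, DOOR probability = 0.5 + 0.5 × [P(no SAE, phage) − P(no SAE, placebo)].

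- ITT N, n = 20, k = 1: 0.5 + 0.5 × (19/20 − 20/20) = 0.475.
- Sputum N, same case: 0.5 + 0.5 × (19/19 − 20/20) = 0.500.

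**Step 3: results.**

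| n per arm | k | ITT N: SAEs | ITT N: DOOR probability (95% CI) | Sputum N: SAEs | Sputum N: DOOR probability (95% CI) |
|---|---|---|---|---|---|
| 20 | 1 | 1/20 (5%) | 0.475 (0.406–0.545) | 0/19 | 0.500 (0.447–0.553) |
| 20 | 2 | 2/20 (10%) | 0.450 (0.369–0.533) | 0/18 | 0.500 (0.446–0.554) |
| 20 | 3 | 3/20 (15%) | 0.425 (0.336–0.519) | 0/17 | 0.500 (0.444–0.556) |
| 25 | 1 | 1/25 (4%) | 0.480 (0.425–0.536) | 0/24 | 0.500 (0.458–0.542) |
| 25 | 2 | 2/25 (8%) | 0.460 (0.395–0.527) | 0/23 | 0.500 (0.458–0.542) |
| 25 | 3 | 3/25 (12%) | 0.440 (0.367–0.516) | 0/22 | 0.500 (0.457–0.543) |

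Each lost event understates the component by 0.5/20 = 0.025 or 0.5/25 = 0.020. Under the sputum N the estimate stays at 0.500 however many such events occur. For one event, the exact (Clopper-Pearson) interval for the SAE rate changes from 0.1–24.9% to 0–17.6% at n = 20, and from 0.1–20.4% to 0–14.2% at n = 25.

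**Step 4: over time.** A subject with a related SAE on the dosing day who gives the 2-hour sample and no more is counted at Day 1 post-infusion (1/20) but is outside N at Days 2, 5 and 8 (0/19). The number of subjects with an SAE would fall as follow-up lengthens.

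**Step 5: where else the same contrast appears.** By the rank definitions, the split of Ranks 1–3 against Rank 4 in Table 31 is no related SAE against related SAE. Scenario A of Table 32 scores Ranks 1–3 as 100 and Rank 4 as 0, so it carries the same contrast. Both give a between-arm estimate with a confidence interval on an ITT N. With Rank 4 as defined, both keep the subject whom Table 33 drops.

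**The case against.** The strongest defence is that this is a mock-up footnote at odds with sound governing text. Section 8 says ITT, 8.1.3 puts no sputum condition on the SAE component, the table's own title says ITT, and a programmer might follow those instead. That limits the severity. It does not remove the error, because the note is explicit, appears in three tables, and is the only statement of N that they carry.

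Stronger readings are tempting, and the documents do not support them:

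- A reader might infer that the event vanishes from the trial's harm count. It does not. It stays in Rank 4 as defined, in the safety summaries (Tables 40 and 51 to 54) and in the SAE listing (Table 56). A related SAE also suspends enrollment and dosing pending DSMB review (Protocol 8.6.1).
- A reader might take Table 33 as the only between-arm estimate of related SAEs with an interval. Table 31 and Table 32 Scenario A also provide one.
- A reader might assume that a halted infusion means no later sputum. Protocol 8.6.2 stops only the infusion, 5.2.1 makes withdrawal possible rather than automatic, 6.3.3 asks sites to try to collect sputum at early termination, and 6.4 supplies kits for virtual visits. Loss of sputum is possible, not certain.
- A reader might extend the loss to the Maximum block, which matches the primary DOOR definition. N is undefined there, and a subject with the 2-hour sample may still be counted.

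The effect is also modest for a single event: both intervals in the one-event case include 0.5.

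**Conclusion.** Wrong as written, in a supporting display; minor to moderate. The stated denominator contradicts the SAP's ITT rule and its definition of the SAE component. It can hide related SAEs in the visit blocks of Table 33 and addendum Tables 26 and 27, and in the Day 8 component forest plot (SAP Figure 10) if that is built from them. The size is 0.025 (n = 20) or 0.020 (n = 25) on the component DOOR probability per lost event. It depends on the assumed events and on the absence of sputum at that visit.

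A reader might go further and infer that the primary composite loses these subjects too. The Rank 4 definition implies otherwise. However, the SAP never says outright that a related SAE without a colony count is Rank 4 rather than missing DOOR. The addendum leaves room for the other reading. It says that five of the 32 interim subjects, for whom no change from baseline could be calculated, contributed nothing to DOOR, without mentioning their SAE status. It also replaces the table of missing DOOR data with one based on colony-count detectability. That is an ambiguity to close; it does not show that the composite is wrong.

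**What to change.** In Table 33 and addendum Tables 26 and 27:

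- For the SAE rows, set N to the ITT population of SAP 6.3.2. Count related SAEs cumulatively from dosing to the time point, and retain them after withdrawal. A new set of ITT subjects who were dosed is not needed and would depart from the SAP's own definition.
- Keep the sputum-based N for the log10-reduction rows only.
- Define N for the Maximum block.

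In 8.1.3, add one sentence: a related SAE by Day 8 + 3 is Rank 4 at that and later DOOR time points even without a colony count, and is not set to missing DOOR.

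The cost is three table notes and one sentence. No new assessment is needed: the protocol already provides for SAE follow-up after withdrawal, where the subject consents (5.2.1). The change should be made before database lock, so that the ranking of a harmed subject without sputum is not decided after the data are seen.
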